**Summary of Protocol Amendment Changes with Rationale**

Protocol Amendment 03 incorporates change in dosing regimen from 60 mg BID to 60 mg TID, restrictions on JAK inhibitors, defined non-reproductive potential criteria in Exclusion 11, change to clinical laboratory criteria in Exclusion 23, of evaluation of joint space narrowing with MRI, flexibility in scheduling with MRI and synovial biopsy.

GlaxoSmithKline Document Number of Investigator Brochure GSK2982772 has been updated to 2014N204126\_02 throughout the document. Other minor protocol clarifications and administrative changes are also provided in this amendment.

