#### 5.1. Inclusion Criteria

A subject will be eligible for inclusion in this study only if all of the following criteria apply:

AGE
1. Between 18 and 75 years of age inclusive, at the time of signing the informed consent.
TYPE OF SUBJECT AND DIAGNOSIS INCLUDING DISEASE SEVERITY
2. Subjects that do not have any medical conditions, other than moderate to severe RA, that in the opinion of the Investigator put the subject at unacceptable risk or interfere with study assessments or integrity of the data. These medical conditions should be

stable at the time of screening and are expected to remain stable for the duration of the study.
 
 
3. Subject has had a confirmed diagnosis of rheumatoid arthritis according to the revised 2010 American College of Rheumatology/European League Against Rheumatism ACR-EULAR classification criteria.
 
4. Disease duration of <math>\geq 12</math> weeks (time from onset of patient-reported symptoms of either pain or stiffness or swelling in hands, feet or wrists) at screening.
 
5. Swollen joint count of <math>\geq 4</math> (28-joint count) and tender joint count <math>\geq 4</math> (28-joint count) at screening.
 
6. Subject has a DAS28 CRP disease activity score of <math>\geq 3.2</math> and CRP <math>\geq 5.0</math> mg/L (<math>\geq 4.76</math> nmol/L) at screening.
 
7. Subject must have received at least 12 weeks of non-biologic DMARD monotherapy or methotrexate (MTX)/DMARD combination therapy prior to screening AND must be on stable dose throughout the study.
 
8. Subject is naive to any biological therapies for RA
 
 
OR
 
Subject may have had previous exposure to a single anti-TNF biologic agent which was discontinued for reasons other than primary non-response more than 8 weeks (or 5 half lives whichever is longer) from first dose. Note: Exposure to a single anti-TNF is not required in addition to Inclusion #7 above.
 
 
9. For subjects who have consented to synovial joint biopsy: 
 
a. Subject has an involved knee, wrist, or ankle suitable for biopsy, as assessed by a rheumatologist at screening.
 
 
 

--

WEIGHT
---------------

10. A body mass index (BMI) within range of 18.5 - 35 kg/m  (inclusive) at screening.
---

SEX
------------

11. Male and female subjects

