## 5.2. Exclusion Criteria

A subject will not be eligible for inclusion in this study if any of the following criteria apply:

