The specific formula that will be used to determine eligibility and discontinuation for an individual subject should be determined and documented prior to initiation of the study. In other words, several different formulae cannot be used to calculate the QTc for an individual subject and then the lowest QTc value used to include or discontinue the subject from the trial. For purposes of data analysis, QTcB, QTcF, another QT correction formula, or a composite of available values of QTc will be used as specified in the Reporting and Analysis Plan (RAP).

5. ALT >2xULN and bilirubin >1.5xULN (isolated bilirubin >1.5xULN is acceptable if bilirubin is fractionated and direct bilirubin <35%) at screening.
6. Current active or chronic history of liver or biliary disease (with the exception of Gilbert's syndrome or asymptomatic gallstones).
7. Current or history of renal disease or estimated glomerular filtration rate (GFR) by Chronic Kidney Disease Epidemiology Collaboration equation (CKD-EPI) calculation <60 mL/min/1.73m^2 at screening.
8. Hereditary or acquired immunodeficiency disorder, including immunoglobulin deficiency.
9. A major organ transplant (e.g., heart, lung, kidney, liver) or hematopoietic stem cell/marrow transplant.
10. Any planned surgical procedures including surgical joint procedures (e.g., intra-articular, tendon sheath, or bursal corticosteroid injections) during the study.
11. A history of malignant neoplasm within the last 5 years, except for adequately treated non-metastatic cancers of the skin (basal or squamous cell) or carcinoma in situ of the uterine cervix that has been fully treated and shows no evidence of recurrence.
12. Has undergone surgery including synovectomy or arthroplasty on the joint chosen for biopsy and/or magnetic resonance imaging (MRI).
13. The subject has a history of any other joint disease other than RA at the knee, wrist or ankle joint chosen for biopsy and/or MRI (e.g., gout, pseudogout, osteoarthritis).
14. Has undergone intra-articular corticosteroid injection, arthrocentesis or synovial biopsy on any joint within 6 weeks of screening.
15. A known allergy to lidocaine or other local anaesthetics (**Note**: only applies to subjects who consent for synovial biopsy procedures).
16. Contraindication to MRI scanning (as assessed by local MRI safety questionnaire) which includes but are not limited to:
  - Intracranial aneurysm clips (except Sugita™) or other metallic objects,

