#### DIAGNOSTIC ASSESSMENTS AND OTHER CRITERIA

23. Haemoglobin <11 g/dL; haematocrit <30%, white blood cell count  $\leq 3,000/\text{mm}^3$  ( $\leq 3.0 \times 10^9/\text{L}$ ) or  $\geq 14,000/\text{mm}^3$  ( $\geq 14 \times 10^9/\text{L}$ ); platelet count  $\leq 100,000/\mu\text{L}$  ( $\leq 100 \times 10^9/\text{L}$ ); absolute neutrophil count  $\leq 3 \times 10^9/\text{L}$ ; lymphocyte count  $< 1 \times 10^9/\text{L}$  at screening.
24. Presence of hepatitis B surface antigen (HBsAg), positive hepatitis C antibody test result at screening or within 3 months prior to first dose of study treatment. As potential for and magnitude of immunosuppression with this compound is unknown, subjects with presence of hepatitis B core antibody (HBcAb) should be excluded.
25. A positive serology for human immunodeficiency virus (HIV) 1 or 2 at screening.
26. Where participation in the study would result in donation of blood or blood products in excess of 500 mL within 3 months.
27. Exposure to more than 4 investigational medicinal products within 12 months prior to the first dose.

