### 5.4. Withdrawal/Stopping Criteria

Subjects may be withdrawn from the study for any of the following reasons:

- A subject may withdraw from study treatment at any time at his/her own request, or may be withdrawn at any time at the discretion of the Investigator for safety, behavioural or administrative reasons. If a subject withdraws from the study, he/she may request destruction of any samples taken, and the Investigator must document this in the site study records. The reason for withdrawal should be documented in the Case Report Form (CRF).
- The Sponsor's request, for reasons such as significant protocol deviations (and after discussion with the Investigator).
- If a subject is withdrawn from study treatment, this subject is also considered to be withdrawn from the study.
- Study is terminated by the Sponsor.

If a subject is withdrawn, the Sponsor may decide to replace that subject and this will be done through the Interactive Response Technology System (IRTS).

If a subject chooses to withdraw from the study after dosing then the Investigator must make every effort to complete the follow-up assessments detailed in the Time and Events Table (Section 7.1).

The following actions must be taken in relation to a subject who fails to attend the clinic for a required study visit:

- The site must attempt to contact the subject and re-schedule the missed visit as soon as possible.

- The site must counsel the subject on the importance of maintaining the assigned visit schedule and ascertain whether or not the subject wishes to and/or should continue in the study.
- In cases where the subject is deemed ‘lost to follow up’, the Investigator or designee must make every effort to regain contact with the subject (where possible, 3 telephone calls and if necessary a certified letter to the subject’s last known mailing address or local equivalent methods). These contact attempts should be documented in the subject’s medical record.
- Should the subject continue to be unreachable, only then will he/she be considered to have withdrawn from the study with a primary reason of “Lost to Follow-up”.

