FSH & estradiol (if applicable)	X														
Serum pregnancy test (WCBP only)	X														
Urine pregnancy test (WCBP only) 		X 	X	X		X		X 		X		X		X	X
Haematology, chemistry, urinalysis	X	X 	X	X		X 		X 		X 		X 		X	X
CRP	X	X 		X		X		X 		X		X		X	X
Blood sample for PD inflammatory biomarkers, mRNA, and TE 		X 						X 						X	X
PK blood samples GSK2982772 		X	X 					X 						X	X
PK blood samples for MTX 		X 	X 					X 							
Pharmacogenetic sample (PGx)		X 													
Synovial biopsies for PK, inflammatory biomarkers, mRNA, target engagement & pathway engagement analysis 		X 						X 							X 

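### Exclusion 5 joins its ALT and bilirubin limits with 'and', so read literally neither limit excludes alone and the isolated-bilirubin exception does nothing

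*Protocol*

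**What the plan says.** Section 5.2 opens with the rule that "A subject will not be eligible for inclusion in this study if any of the following criteria apply". Exclusion 5 then reads "ALT >2xULN and bilirubin >1.5xULN (isolated bilirubin >1.5xULN is acceptable if bilirubin is fractionated and direct bilirubin <35%) at screening".

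Three other visible entry criteria bear on the liver:

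- Exclusion 6: "Current active or chronic history of liver or biliary disease (with the exception of Gilbert's syndrome or asymptomatic gallstones").
- Exclusion 24, on viral hepatitis: "Presence of hepatitis B surface antigen (HBsAg), positive hepatitis C antibody test result at screening", with hepatitis B core antibody also excluded.
- Inclusion 2, which turns away subjects whose other medical conditions "in the opinion of the Investigator put the subject at unacceptable risk" or interfere with the study.

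Appendix 2 (Section 12.2) lists the liver stopping criteria, with the same values in the original and amended texts. ALT of 5xULN or more stops treatment whatever the bilirubin. ALT of 3xULN or more stops it when combined with raised bilirubin, raised INR, symptoms, persistence for at least four weeks, or inability to monitor weekly.

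The Section 5 preamble forbids deviations from the entry criteria and calls for adherence to them as written.

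**The concern.** The criterion contradicts itself. An exception for isolated bilirubin makes sense only if raised bilirubin alone would otherwise exclude, and under 'and' it would not. A site that follows the text admits isolated ALT elevation of any height as far as this criterion goes. A site that guesses the likely intention applies a different rule, and departs from wording that the preamble tells it to follow.

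Safety and tolerability is the primary objective, and clinical chemistry is among the primary endpoints. Table 1 in Section 6.11.1 permits methotrexate and leflunomide as background treatment. The risk table in Section 4.6.1 notes a low risk that the study drug could impair methotrexate clearance, and names liver function tests as part of the monitoring. A numeric ALT limit at entry is therefore worth having, and the text as written does not supply one for isolated elevation.

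**Working it through.** The check is one of logic, not of sample size or power, and the plan has no figure to reproduce.

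**Inputs.** From exclusion 5, let A = ALT above 2xULN, B = bilirubin above 1.5xULN, and F = bilirubin fractionated with the direct part below 35%. I take isolated bilirubin to mean B without A. From the lead-in, meeting any one criterion excludes.

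**Literal reading.** Excluded = (A and B), less the exception (B and not A and F). The first term needs A and the exception needs not-A. They cannot both hold, so the exception removes nobody.

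**Alternative reading.** Excluded = (A or B), less the exception (B and not A and F). Here the exception has work to do.

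| ALT >2xULN | Bilirubin >1.5xULN | Direct part <35% on fractionation | Excluded under 'and' | Excluded under 'or' |
|---|---|---|---|---|
| no | no | any | no | no |
| no | yes | yes | no | no (spared by the exception) |
| no | yes | no, or not done | no | yes |
| yes | no | any | no | yes |
| yes | yes | any | yes | yes |

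The two readings differ in the third and fourth rows: isolated bilirubin that the exception does not cover, and isolated ALT. These rows are logical cases and say nothing about how often each occurs.

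**How the protocol uses 'and' elsewhere.** In exclusion 1 (a positive anti-dsDNA result together with a lupus diagnosis) both conditions are needed. The same holds for the combined ALT and bilirubin stopping rule in Appendix 2. Where separate limits are meant, exclusion 4 uses 'or', and exclusion 23 uses semicolons and 'or'. A conjunctive reading of exclusion 5 is therefore the natural literal one.

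**Against the stopping limits.** Take ALT at 5xULN with bilirubin normal. A is true and B is false, so (A and B) is false and criterion 5 is passed. The same ALT already meets the absolute ALT stopping criterion. ALT from 3xULN to below 5xULN with normal bilirubin also passes, and would meet a stopping criterion if it persisted for four weeks or more. Under 'or' the screening ceiling is 2xULN, below 3xULN, the lowest ALT value in any stopping criterion.

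**Backstops.** Inclusion 2 rests on the Investigator's opinion, exclusion 6 on liver or biliary disease, and exclusion 24 on hepatitis serology. None contains an ALT or bilirubin threshold.

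**The case against.** **Version.** The full text of exclusion 5 stands in the original protocol (twice-daily dosing, about 30 subjects). The amended text available begins within Section 6.11.2, so the current Section 5.2 cannot be read. Some Section 5.2 criteria did change, and Amendments 1 to 3 each mention other minor clarifications. This objection stands in part. The visible Section 5.2 entries in Appendix 8 for Amendments 1, 3 and 4 leave exclusion 5 alone, and the Amendment 3 summary names, for laboratory entry criteria, only the "change to clinical laboratory criteria in Exclusion 23". Not every part of the amendment log is available, so carry-over is likely but unconfirmed.

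**Recoverable intention.** The exception itself points to 'or', and many sites may apply it that way. That is fair, but it leaves entry to a guess in a protocol that asks for adherence to the criteria as written.

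**Other safeguards.** Admission at 5xULN would also have to get past inclusion 2 and exclusions 6 and 24. The Investigator judges the clinical significance of out-of-range results (Section 7.3), and clinically significant abnormal values are to be repeated (notes to Table 3). The row "Haematology, chemistry, urinalysis" in Section 7.1 schedules chemistry before dosing on Day 1 and then on Days 8, 15, 29, 43, 57, 71 and 85. These checks make the extreme case less likely. They do not replace a numeric limit at screening, and the scheduled on-study samples begin only on Day 1.

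**A stronger inference to avoid.** Section 5.4 says "If a subject is withdrawn from study treatment, this subject is also considered to be withdrawn from the study", and a reader might infer that every subject stopped under the liver rules is lost to the study, at a fixed cost to the sample. The document does not settle that. After a liver stopping event, Appendix 2 allows a subject who has permanently discontinued treatment to continue in the study for protocol-specified follow-up. Section 5.4 itself asks for every effort to complete follow-up assessments and allows replacement.

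**Conclusion.** The point holds as a defect in the wording of exclusion 5. Read literally, it excludes only subjects above both limits, its exception has no effect, and isolated ALT at or above the 5xULN stopping limit can pass it. It should be corrected, because it is an eligibility rule in a trial whose primary objective is safety.

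Its size can be stated only as the kinds of subject left without a numeric limit: isolated ALT above 2xULN, and isolated bilirubin above 1.5xULN that is unfractionated or at least 35% direct. The document gives no screening distribution of ALT or bilirubin, so no number of subjects and no share of the sample can be derived. Nor does it show that any such subject was enrolled.

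The conclusion rests on two assumptions: that 'and' is conjunctive here, as elsewhere in the protocol, and that exclusion 5 as it stands in the April 2016 protocol carries over into the current Section 5.2.

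**What to change.** Check exclusion 5 in the current Section 5.2. If the wording is unchanged, replace the 'and' between the ALT limit and the bilirubin limit with 'or', leaving both thresholds, the bracketed exception and the timing at screening as they are. Each limit then excludes alone, the exception spares isolated, predominantly indirect bilirubin elevation, and ALT at entry is held below every ALT value in the stopping criteria.

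The cost is one word in an amendment and possibly a few more screen failures. Section 5.3 already lets a subject who fails on a laboratory value repeat the test once within the screening window, which limits losses from transient elevations.

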#### CONCOMITANT MEDICATIONS

17. The subject has received treatment with the therapies listed in Section 6.11.2, or changes to those treatments, within the prescribed timeframe. If in doubt, or the therapy is not listed please consult with the medical monitor.
- Other medications (including vitamins, herbal and dietary supplements) will be considered on a case-by-case basis, and will be allowed if in the opinion of the Investigator the medication will not interfere with the study procedures or compromise subject safety.

#### RELEVANT HABITS

18. History of alcohol or drug abuse that would interfere with the ability to comply with the study.

#### CONTRAINDICATIONS

19. History of sensitivity to any of the study treatments, or components thereof or a history of drug or other allergy that, in the opinion of the Investigator or Medical Monitor, contraindicates their participation.
20. Received a live or attenuated vaccine within 30 days of randomization OR plan to receive a vaccination during the study until half-lives (or 2 days) plus 30 days after receiving GSK2982772.
21. Contraindication to gadolinium contrast agent in accordance with local guidelines.
22. The subject has participated in a clinical trial and has received an investigational product within 30 days or 5 half-lives, whichever is longer before the first dose of study medication, or plans to take part in another clinical trial at the same time as participating in this clinical trial.

#### DIAGNOSTIC ASSESSMENTS AND OTHER CRITERIA

23. Haemoglobin <11 g/dL; haematocrit <30%, white blood cell count  $\leq 3,000/\text{mm}^3$  ( $\leq 3.0 \times 10^9/\text{L}$ ) or  $\geq 14,000/\text{mm}^3$  ( $\geq 14 \times 10^9/\text{L}$ ); platelet count  $\leq 100,000/\mu\text{L}$  ( $\leq 100 \times 10^9/\text{L}$ ); absolute neutrophil count  $\leq 3 \times 10^9/\text{L}$ ; lymphocyte count  $< 1 \times 10^9/\text{L}$  at screening.
24. Presence of hepatitis B surface antigen (HBsAg), positive hepatitis C antibody test result at screening or within 3 months prior to first dose of study treatment. As potential for and magnitude of immunosuppression with this compound is unknown, subjects with presence of hepatitis B core antibody (HBcAb) should be excluded.
25. A positive serology for human immunodeficiency virus (HIV) 1 or 2 at screening.
26. Where participation in the study would result in donation of blood or blood products in excess of 500 mL within 3 months.
27. Exposure to more than 4 investigational medicinal products within 12 months prior to the first dose.

### 5.3. Screening/Baseline/Run-in Failures

Screen failures are defined as subjects who consent to participate in the clinical trial but are never subsequently randomized. In order to ensure transparent reporting of screen failure subjects, meet the Consolidated Standards of Reporting Trials (CONSORT) publishing requirements, and respond to queries from Regulatory authorities, a minimal set of screen failure information is required including Demography, Screen Failure details, Eligibility Criteria, and Serious Adverse Events and protocol deviations (see Section 7.3.1.5).

Subjects who do not qualify to participate in the study due to a screening laboratory value or ECG abnormality can repeat the test once within the original screening window, if the Investigator believes there is a reasonable possibility that the subject would be eligible if re-tested.

Subjects can be re-screened only on approval of the GSK Medical Monitor and only once. Re-screening is allowed when a subject failed inclusion/exclusion criteria or some other screening condition initially, but the Investigator believes there is a reasonable probability that the subject would be eligible if re-screened.

### 5.4. Withdrawal/Stopping Criteria

Subjects may be withdrawn from the study for any of the following reasons:

- A subject may withdraw from study treatment at any time at his/her own request, or may be withdrawn at any time at the discretion of the Investigator for safety, behavioural or administrative reasons. If a subject withdraws from the study, he/she may request destruction of any samples taken, and the Investigator must document this in the site study records. The reason for withdrawal should be documented in the Case Report Form (CRF).
- The Sponsor's request, for reasons such as significant protocol deviations (and after discussion with the Investigator).
- If a subject is withdrawn from study treatment, this subject is also considered to be withdrawn from the study.
- Study is terminated by the Sponsor.

If a subject is withdrawn, the Sponsor may decide to replace that subject and this will be done through the Interactive Response Technology System (IRTS).

If a subject chooses to withdraw from the study after dosing then the Investigator must make every effort to complete the follow-up assessments detailed in the Time and Events Table (Section 7.1).

The following actions must be taken in relation to a subject who fails to attend the clinic for a required study visit:

- The site must attempt to contact the subject and re-schedule the missed visit as soon as possible.

- The site must counsel the subject on the importance of maintaining the assigned visit schedule and ascertain whether or not the subject wishes to and/or should continue in the study.
- In cases where the subject is deemed ‘lost to follow up’, the Investigator or designee must make every effort to regain contact with the subject (where possible, 3 telephone calls and if necessary a certified letter to the subject’s last known mailing address or local equivalent methods). These contact attempts should be documented in the subject’s medical record.
- Should the subject continue to be unreachable, only then will he/she be considered to have withdrawn from the study with a primary reason of “Lost to Follow-up”.

#### **5.4.1. Individual Safety Stopping Criteria**

Study medication will be discontinued in the event of any of the following:

- If a subject experiences a serious or severe clinically significant AE that in the clinical judgement of the Investigator, after consultation with the medical monitor, is possibly, probably or definitely related to investigational product.
- The subject becomes pregnant.
- The subject initiates treatment with any prohibited medications for the treatment of RA as listed in Section 6.11.2.
- The subject develops a serious opportunistic or atypical infection.
- If any of the liver chemistry stopping criteria (Section 5.4.3), QTc stopping criteria (Section 5.4.4), or Haematologic stopping criteria (Section 5.4.5) are met.

